Hip Abduction (13)	R & L	$195.24 - 62.4(1-gender) - 1.184(age) + .198 (weight \times 9.8067)$
Knee Flexion (12)	R	$9.8067 [-(age \times .16) + (gender \times 8.78) + ((weight/height^2) \times .08) + 22.47]$
Knee Flexion (12)	L	$9.8067 [-(age \times .17) + (gender \times 7.67) + ((weight/height^2) \times .14) + 21.10]$
Knee Extension (12)	R	$9.8067 [-(age \times .38) + (gender \times 18.44) + ((weight/height^2) \times .62) + 34.41]$
Knee Extension (12)	L	$9.8067 [-(age \times .38) + (gender \times 17.68) + ((weight/height^2) \times .62) + 33.61]$
Ankle Dorsiflexion (12)	R	$9.8067 [-(age \times .12) + (gender \times 7.93) + ((weight/height^2) \times .11) + 22.87]$
Ankle Dorsiflexion (12)	L	$9.8067 [-(age \times .13) + (gender \times 8.12) + ((weight/height^2) \times .15) + 21.91]$

* Age in years; gender: male=1, female=0; weight in kgs; height in meters.

Table 8 - Pediatric muscle strength reference values in Newton (N) (14)

Muscle Group	Gender	Age												
		4	5	6	7	8	9	10	11	12	13	14	15	16
Hip flexors	Boy			182	182	225	232	261	245	198	289	337	301	395
	Girl			162	184	175	195	177	264	232	308	281	288	301
Hip abductors	Boy			128	124	131	153	174	151	158	225	306	356	312
	Girl			109	122	117	124	104	140	171	227	244	257	244
Knee extensors	Boy			156	157	185	194	267	239	225	296	370	362	396
	Girl			148	177	166	173	198	265	250	346	280	325	373
Knee flexors	Boy	111	105	158	180	185	195	268	218	201	273	307	327	382
	Girl	92	99	154	171	160	180	175	246	221	301	271	282	336
Foot dorsal flexors	Boy	71	76	104	130	137	141	154	149	170	218	257	267	291
	Girl	75	76	95	114	121	137	130	178	177	214	207	220	232

Table 9 - Pediatric muscle strength reference values in Newton (N) (15)

Muscle Group	Gender	Age Groups					
		3.5-5.5	5.5-7.5	7.5-9.5	9.5-11.5	11.5-13.5	13.5-15
Hip extensors	Boy	80	131	170	210	226	277
	Girl	76	124	157	174	226	267

If a patient is not covered by one of the reference equations, specifically 15-16 years old for hip extension, the reference equation for the oldest age group available (13.5-15 years) will be used.

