This assessment will include the expanded and revised Gross Motor Function Classification System for the GMFM-88 (gross motor function classification system-expanded and revised [GMFCS-E&R]) adapted for adults (21). The GMFCS emphasizes concepts in the World Health Organization's International Classification of Functioning, Disability and Health. Emphasis is on performance in home, work and community settings without judgments about quality of movement or prognosis for improvement. The GMFCS is a 5 level classification system consisting of Levels I to V based on self-initiated movement, with emphasis on sitting, transfers, and mobility. The distinctions between levels are based on functional limitations, the need for

assistive mobility devices, and to a much lesser extent, quality of movement, and are designed to be meaningful in daily life (21).

The general headings for the 5 levels (analyzed as 1, 2, 3, 4, 5) are:

- Level I Walks without limitations,
- Level II Walks with limitations,
- Level III Walks using a hand-held mobility device,
- Level IV Self-mobility with limitations; may use powered mobility,
- Level V Transported in a manual wheelchair.

Hand-held dynamometry (upper extremity muscle strength)

Upper extremity strength in the following muscle groups will be included:

- Shoulder Flexion,
- Shoulder Extension,
- Shoulder Abduction,
- Shoulder Adduction,
- Elbow Flexion,
- Elbow Extension,
- Grip Strength.

The limb tests will be completed bilaterally to account for differences in the generated force for the dominant and nondominant limb. Every muscle group will be measured two times and the highest value will be reported in the e-CRF. Patients may use noninvasive ventilation during the dynamometry assessment.

The summary score of the upper extremity strength will be the sum of the 14 measurements from the 7 muscle groups (left and right measurements from each muscle group). If any of the 14 measurements from the 7 muscle groups in extremity strength is missing, the summary score of the upper extremity strength is missing.

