The percent predicted muscle strength will be calculated separately for muscle groups for which percent predicted equations are available; the percent predicted value of the total score for the upper extremity strength will be the average of the 12 percent predicted values from the 6 muscle groups. If any of the 12 measurements from the 6 muscle groups in percent predicted total score is missing, the percent predicted total score is not available.

No healthy predicted values are available for shoulder adduction for adults thus the following 6 muscle groups (both left and right side) are used in calculating the summary score.

- Shoulder Flexion,
- Shoulder Extension,
- Shoulder Abduction,
- Elbow Flexion,

- Elbow Extension,
- Grip Strength.

The reference equations to determine healthy predicted results for each muscle group are provided in [Table 10](#), [Table 11](#), and [Table 12](#). For the patients with age >16 at baseline, the predicted muscle strength will be calculated using the adult reference equations in [Table 7](#). For the patients with baseline age between 3 and 16 years old, the predicted muscle strength will be calculated using the pediatric reference questions in [Table 11](#) and [Table 12](#). For pediatric patients, the same reference equations will be used to calculate the predicted results from both left and right sides within each muscle group. For patients with baseline age between 3 and 16 years old, the predicted muscle strength normal reference is not available for shoulder flexion, shoulder extension, and shoulder adduction from existing publications; therefore, the summary score of the upper extremity muscle strength and supper extremity strength percent predicted will not be calculated.

Table 10 - ADULT HHD Reference Equations to Determine Healthy Predicted Result (N) (12) (13)

Muscle / Action (Reference)	Age=years; Gender: Male=1, Female=0; weight=kg, height=meters
Shoulder Flexion, Right, Left (1)	R: $9.8067 [-(age \times .14) + (gender \times 11.22) + ((weight/height^2) \times .22) + 16.85]$ L: $9.8067 [-(age \times .12) + (gender \times 10.68) + ((weight/height^2) \times .24) + 14.68]$
Shoulder Extension, Right, Left (1)	R: $9.8067 [-(age \times .17) + (gender \times 16.26) + ((weight/height^2) \times .17) + 23.35]$ L: $9.8067 [-(age \times .18) + (gender \times 14.64) + ((weight/height^2) \times .29) + 19.59]$

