Elbow Flexion, Right, Left (1)	R: $9.8067 [-(age \times .13) + (gender \times 11.24) + ((weight/height^2) \times .07) + 22.78]$ L: $9.8067 [-(age \times .11) + (gender \times 10.63) + ((weight/height^2) \times .05) + 19.66]$
Elbow Extension, Right, Left (1)	R: $9.8067 [-(age \times .08) + (gender \times 8.33) + ((weight/height^2) \times .16) + 12.37]$ L: $9.8067 [-(age \times .07) + (gender \times 8.18) + ((weight/height^2) \times .17) + 11.32]$
Grip Strength, Right, Left (1)	R: $[-(age \times .18) + (gender \times 16.90) + ((weight/height^2) \times .23) + 31.33] / 2.20$ L: $[-(age \times .16) + (gender \times 16.68) + ((weight/height^2) \times .29) + 26.60] / 2.20$
Shoulder Abduction, Right, Left (2)	$178.90 - 77.1(gender) - 1.128(age) + .134(9.8067 \times weight)$

Table 11 - Pediatric muscle strength reference values in Newton (N) (14)

Muscle Group	Gender	Age												
		4	5	6	7	8	9	10	11	12	13	14	15	16
Shoulder Abductors	Boy	62	55	97	92	98	110	136	110	118	159	205	219	253
	Girl	68	47	75	91	94	91	81	129	123	154	178	173	173
Elbow Extensors	Boy			73	85	90	89	120	103	104	128	158	175	182
	Girl			73	85	82	91	84	108	117	118	129	141	107
Elbow Flexors	Boy	78	70	103	121	124	134	173	153	160	195	253	287	276
	Girl	69	66	105	103	115	125	134	172	168	201	193	198	215

Table 12 - Pediatric grip strength reference values (Mathiowetz, et al, 1986) (22)

Average Performance of Normal Subjects on Grip Strength (lb)

Age	Hand	Males			Females		
		Mean	SD	Range	Mean	SD	Range
6-7	R	32.5	4.8	21-42	28.6	4.4	20-39
	L	30.7	5.4	18-38	27.1	4.4	16-36
8-9	R	41.9	7.4	27-61	35.3	8.3	18-55
	L	39.0	9.3	19-63	33.0	6.9	16-49
10-11	R	53.9	9.7	35-79	49.7	8.1	37-82
	L	48.4	10.8	26-73	45.2	6.8	32-59
12-13	R	58.7	15.5	33-98	56.8	10.6	39-79
	L	55.4	16.9	22-107	50.9	11.9	25-76
14-15	R	77.3	15.4	49-108	58.1	12.3	30-93
	L	64.4	14.9	41-94	49.3	11.9	26-73
16-17	R	94.0	19.4	64-149	67.3	16.5	23-126
	L	78.5	19.1	41-123	56.9	14.0	23-87
18-19	R	108.0	24.6	64-172	71.6	12.3	46-90
	L	93.0	27.8	53-149	61.7	12.5	41-86

Note: The mean scores for individuals, aged 14 to 19 years, may be slightly low (0-10 lb lower than they should be) due to instrument error detected after the study.

5-Level EuroQol in 5 dimensions

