2.5.1.3 Hand-held dynamometry (lower extremity muscle strength)

Change from baseline in lower extremity muscle strength composite score will be analyzed based on the MMRM model, similar to the primary endpoint described in [Section 2.5.1](#). The model will include summary HHD lower extremity score at baseline, baseline FVC (% predicted) and age (as continuous variables), gender (male or female), treatment group, visit, and treatment-by-visit interaction as fixed effects.

As a supportive analysis, change from baseline in % predicted of the summary score for the lower extremity muscle strength will be analyzed based on the MMRM model, similar to the primary endpoint described in [Section 2.5.1](#). The model will include the % predicted of the summary score at baseline, baseline FVC (% predicted), and age (as continuous variables), gender (male or female), treatment group, visit, baseline HHD % predicted score-by-visit interaction and treatment-by-visit interaction as fixed effects. Similar analyses on the % predicted for each muscle group will be conducted.

Since % predicted values are only available for all muscle groups for patients age 6 or older, the analysis on % predicted HHD lower extremity summary will be performed in mITT patients with an age of 6 or older.

Raw score as well as the % predicted scores for each muscle group will also be summarized descriptively by treatment group and study visit.

In order to evaluate quality of observed changes in muscle strength measured with HHD, a sub-group analysis of HHD data will be performed of data confirmed to be collected by same assessor and with the patient in the same position as baseline and Week 49. HHD outcomes will include all muscle groups and UE and LE composites.

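### Two adult equations in SAP Table 10 (shoulder abduction and grip) give wrong predicted values as printed, so the upper-extremity percent-predicted average is wrong

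*SAP*

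**What the plan says.** SAP 2.1.3.3 defines percent predicted for upper-extremity hand-held dynamometry (HHD). The adult equations are in Table 10, titled "ADULT HHD Reference Equations to Determine Healthy Predicted Result (N") and coded "Age=years; Gender: Male=1, Female=0; weight=kg, height=meters".

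- **Shoulder abduction, both sides:** the equation begins "178.90 - 77.1(gender) - 1.128(age") and adds 0.134 × 9.8067 × weight.
- **Grip:** a linear bracket in age, gender and BMI is divided by 2.20. The shoulder flexion, shoulder extension, elbow flexion and elbow extension rows multiply a bracket of the same form by 9.8067.
- **Composite:** the percent-predicted total "will be the average of the 12 percent predicted values from the 6 muscle groups". Shoulder abduction and grip, right and left, are four of these twelve.
- **Cross-reference:** one sentence names Tables 10 to 12, but the next sends patients older than 16 to Table 7, which holds only lower-limb equations.

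On use, SAP 2.5.1.3 plans a same-assessor, same-position HHD analysis: "HHD outcomes will include all muscle groups and UE and LE composites". SAP 2.5.5 analyses the other exploratory efficacy endpoints by a method similar to the primary one.

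**The concern.** A healthy reference value should put adult men above adult women in shoulder strength, and should be in the unit of the measurement it divides. Neither holds for these rows. A program that follows the table would give percent-predicted values wrong in opposite directions for the two sexes (shoulder abduction) and too high for everyone (grip). It would also let grip carry far more than its intended one-sixth of the composite, so neither the level of the composite nor a change in it could be interpreted.

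**Working it through.** The SAP prints no worked predicted value, so there is no figure to reproduce. The check evaluates the equations as printed and compares them with other SAP tables. Body weights and BMI are assumptions.

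**Shoulder abduction: internal comparators**

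- Table 7 hip abduction uses the same gender coding but reads "195.24 - 62.4(1-gender) - 1.184(age"), so the deduction falls on women.
- Every other Table 10 equation adds a positive male term.
- Table 11 at age 16 gives boys 253 N and girls 173 N.

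Printed form: 178.90 − 77.1 × gender − 1.128 × age + 0.134 × 9.8067 × weight. Alternative: replace gender with (1 − gender) in the second term.

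| Case | Printed | With (1 − gender) |
|---|---|---|
| Man, 17 y, 70 kg | 174.6 N | 251.7 N |
| Woman, 17 y, 57 kg | 234.6 N | 157.5 N |
| Man, 48 y, 80 kg | 152.8 N | 229.9 N |
| Woman, 48 y, 65 kg | 210.2 N | 133.1 N |

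For the 48-year-old man: 178.90 − 77.1 − 54.14 + 105.13 = 152.8. At 17 the printed form reverses the ordering in Table 11, while the (1 − gender) form comes close to it. Using +77.1 × gender instead gives about 322 N for a 17-year-old man of 65 kg and 232 N for a woman of 55 kg, well above Table 11.

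Percent predicted is multiplied by s = 229.9/152.8 = 1.505 for the 48-year-old man and s = 133.1/210.2 = 0.633 for the woman.

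**Grip: which unit is the bracket in?**

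Right: −0.18 × age + 16.90 × gender + 0.23 × BMI + 31.33. Left: −0.16 × age + 16.68 × gender + 0.29 × BMI + 26.60. Evaluated at age 18, BMI 22. Table 12 (ages 18–19) is in pounds, "Average Performance of Normal Subjects on Grip Strength (lb"), and is converted at 0.4536 kg per lb.

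| | Bracket | Table 12, kg | Ratio to kg | Ratio to lb | Printed (bracket ÷ 2.20) |
|---|---|---|---|---|---|
| Men R | 50.05 | 49.0 | 1.02 | 0.46 | 22.7 |
| Men L | 46.78 | 42.2 | 1.11 | 0.50 | 21.3 |
| Women R | 33.15 | 32.5 | 1.02 | 0.46 | 15.1 |
| Women L | 30.10 | 28.0 | 1.08 | 0.49 | 13.7 |

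The bracket is therefore already about kilograms. Over BMI 18.5 to 30 the right-hand bracket moves only from 49.2 to 51.9 (men) and from 32.3 to 35.0 (women). The printed results lie below the lowest normal subject in Table 12 even when read as kg (minima 29.0, 24.0, 20.9 and 18.6 kg), and further below if read as lb or N.

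Inflation factor k for grip percent predicted, by recording unit:

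- kg: 2.20
- lb: 2.20/0.4536 = 4.85
- N: 2.20 × 9.8067 = 21.57

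**Effect on the composite**

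Suppose all 12 values are truly 60%. The composite reads (8 × 60 + 2 × 60s + 2 × 60k)/12 = 40 + 10s + 10k. Grip's share is 2k/(8 + 2s + 2k), against an intended 2/12 = 17%.

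| Grip recorded in | Man 48 y, 80 kg | Woman 48 y, 65 kg | Grip share (man, woman) |
|---|---|---|---|
| kg | 77.0 | 68.3 | 29%, 32% |
| lb | 103.5 | 94.8 | 47%, 51% |
| N | 270.8 | 262.1 | 80%, 82% |

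**The case against.** The strongest counter-case concerns reach and certainty.

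- **Analysis affected.** Section 2.5.1.3 speaks of composites without saying percent predicted, and elsewhere in that section the lower-limb composite is the raw score. This is fair for the composite. The derivation of the 12-value average is nevertheless prescribed in 2.1.3.3, and 2.5.5 covers the remaining exploratory endpoints.
- **Sources.** The Table 10 rows cite (1) and (2), which in the SAP reference list are an outcomes review and a non-inferiority-margin paper. Only the table title points to 12 and 13. That shoulder abduction shares source 13 with Table 7 is thus an inference, and the row citations also need repair. The contradiction with Table 11 does not depend on it.
- **Table 12 caveat.** Its note says means at ages 14 to 19 may be up to 10 lb too low. Adding 10 lb gives 53.5, 46.7, 37.0 and 32.5 kg, so the bracket runs from about 10% below to 11% above Table 12. It remains on the kg scale.
- **Magnitude.** The wide range for grip comes from an unstated recording unit, and the 60% is illustrative. Both are true, but no unit makes the printed equation plausible.
- **Literal reading.** Followed word for word, the text sends adults to Table 7, which has no upper-limb equations. The figures here assume Table 10 is what is programmed.
- **Importance.** Upper-extremity strength is a tertiary endpoint outside the testing hierarchy. This limits the consequence but does not make the equations right.

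**Conclusion.** The concern holds. Followed as printed, both Table 10 equations give wrong healthy reference values, as the SAP's own tables show. Adult percent predicted for these two groups, and the 12-value average, would be wrong in absolute level and in the weight given to each muscle group. A given change in shoulder abduction force would count about 2.4 times as much (1.505/0.633) in the example man as in the example woman, relative to the corrected form. The gender main effect in a model similar to the primary one would not undo that scaling.

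There is no systematic between-arm bias: the errors apply alike in both arms, sex is a stratification factor for ex-Japan adults, and gender is in the model. These equations do not enter the primary endpoint, the hierarchical secondary tests, the other four muscle groups or the raw score ("The summary score of the upper extremity strength will be the sum of the 14 measurements from the 7 muscle groups"). The raw sum still depends on the unstated grip unit, because it would mix units if grip were recorded differently from the rest.

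The exact corrections rest on cited sources that were not available here. The sizes rest on the assumed body measurements and recording unit.

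**What to change.** 1. Verify both equations against cited sources 12 and 13, and correct the row citations in Table 10.
2. Unless the sources show otherwise, change the shoulder abduction term to 77.1 × (1 − gender), and replace the grip division by 2.20 with multiplication by 9.8067 so that the prediction is in N, as the table title states.
3. State the unit in which grip is recorded, and use one unit for measured and predicted values and in the raw sum.
4. Change the adult cross-reference from Table 7 to Table 10.
5. Check the derivation programs for the same errors, and re-run the upper-extremity percent-predicted derivation if they are present.

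The cost is a table correction in the SAP and a check or re-run of one derivation. No new data are needed.

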2.1.4 Safety endpoints

The safety analysis will be based on the reported adverse events and other safety information, such as clinical laboratory data, vital signs, ECG, physical examination, weight, height, and immunogenicity.

Observation period

The observation period will be divided into the following epochs:

- The pre-treatment epoch is defined as the time from the signed informed consent date up to first administration of IMP.
- The treatment epoch for PAP is defined as the time from the first administration of the study drug to,
 - The time just prior to the first administration of the study drug in ETP, or,
 - Up to four weeks (28 days) after the last infusion date if the patient does not go to ETP. If the patient enrolls in another study or receives commercially available ERT, the follow-up period may be reduced from 4 to 2 weeks.
- The treatment epoch for ETP is defined as the time from the first administration of the study drug in ETP to the last administration of the study drug + up to 4 weeks (28 days). If the patient enrolls in another study or receives commercially available ERT, the follow-up period may be reduced from 4 to 2 weeks.
- The post treatment epoch for PAP is defined as the time beyond the treatment epoch in PAP through the last study assessment; this epoch is defined only for patients who do not receive any infusion in ETP.
- The post treatment epoch for ETP is defined as the time beyond the treatment epoch in ETP through the last study assessment, defined only for patients who receive any infusion in ETP.

The on-study observation period is pre-treatment, treatment and post treatment epoch.

2.1.4.1 Adverse events variables

Adverse event observation period

- Pretreatment adverse events are adverse events that developed or worsened or became serious from the signed informed consent date up to first administration of IMP.
- Treatment-emergent adverse events are adverse events that developed or worsened or became serious during the treatment-emergent period. More specifically,
 - Treatment-emergent adverse events for PAP are adverse events that developed or worsened or became serious during the treatment epoch for PAP.

- Treatment-emergent adverse events for ETP are adverse events that developed or worsened or became serious during the treatment epoch for ETP, defined for those patients who receive any infusion in ETP.
- Post-treatment adverse events in PAP are adverse events that developed or worsened or became serious during post treatment epoch in PAP and could only be observed in patients who do not get an infusion in ETP.
- Post-treatment adverse events in ETP are adverse events that developed or worsened or became serious during the post treatment epoch for ETP and could only be observed in for patients who receive at least one infusion in ETP.

All adverse events (including serious adverse events [SAE] and adverse events of special interest) will be coded to a lower-level term (LLT), preferred term (PT), high-level term (HLT), high-level group term (HLGT), and associated primary system organ class (SOC) using the version of Medical Dictionary for Regulatory Activities (MedDRA) currently in effect at Sanofi at the time of database lock.

Serious adverse events

An SAE is any untoward medical occurrence that at any dose:

- Results in death, or,
- Is life-threatening, or,
Note: The term “life-threatening” in the definition of “serious” refers to an event in which the patient was at risk of death at the time of the event; it does not refer to an event which hypothetically might have caused death if it were more severe.
- Requires inpatient hospitalization or prolongation of existing hospitalization, or,
- Results in persistent or significant disability/incapacity, or,
- Is a congenital anomaly/birth defect,
- Is a medically important event.
Medical and scientific judgment should be exercised in deciding whether expedited reporting is appropriate in other situations, such as important medical events that may not be immediately life-threatening or result in death or hospitalization but may jeopardize the patient or may require medical or surgical intervention (ie, specific measures or corrective treatment) to prevent one of the other outcomes listed in the definition above.

Note: The following list of medically important events is intended to serve as a guideline for determining which condition has to be considered a medically important event. The list is not intended to be exhaustive:

- Intensive treatment in an emergency room or at home for:
 - Allergic bronchospasm,
 - Blood dyscrasias (ie, agranulocytosis, aplastic anemia, bone marrow aplasia, myelodysplasia, pancytopenia, etc),

- Convulsions (seizures, epilepsy, epileptic fit, absence, etc).
- Development of drug dependence or drug abuse,
- ALT >3 x upper limit of normal (ULN) + total bilirubin >2 x ULN or asymptomatic ALT increase >10 x ULN,
- Suicide attempt or any event suggestive of suicidality,
- Syncope, loss of consciousness (except if documented as a consequence of blood sampling),
- Bullous cutaneous eruptions.

Adverse event of special interest (AESI)

An adverse event of special interest (AESI) is an AE (serious or non-serious) of scientific and medical concern specific to the Sponsor's product or program, for which ongoing monitoring and immediate notification by the Investigator to the Sponsor is required. Such events may require further investigation in order to characterize and understand them.

AESIs will include:

- Infusion-associated reactions:

IARs are defined as AESIs that occur during either the infusion or the observation period following the infusion which are deemed to be related or possibly related to the IMP. At the discretion of the Investigator, AEs occurring after completion of the post-infusion observation period that are assessed as related may also be considered IARs. See more detailed definition in [Section 2.1.5](#).

- Pregnancy:
 - Pregnancy occurring in a female patient included in the clinical trial. Pregnancy will be recorded as an AESI with immediate notification in all cases. It will be qualified as an SAE only if it fulfills the SAE criteria.
 - Male patients will be instructed to notify the Investigator immediately if they discover that their sexual partner is pregnant.
 - In the event of pregnancy in a female participant, IMP should be discontinued.
 - Follow-up of the pregnancy is mandatory in a female participant or in a female partner of a male participant, until the outcome has been determined.
- Symptomatic overdose (serious or nonserious) with IMP:
 - An overdose (accidental or intentional) with the IMP is an event suspected by the Investigator or spontaneously notified by the patient and defined as at least twice the intended dose within the protocol defined therapeutic interval, adjusted according to the tested drug.
Of note, asymptomatic overdose has to be reported as a standard AE.

- Clinical laboratory (change from baseline):
 - ALT or AST increase of ≥ 3 x the ULN if baseline is $< \text{ULN}$, or ALT or AST increase ≥ 2 x the baseline value if baseline is $\geq \text{ULN}$,
 - A maximum ALT value of ≥ 400 IU/L or AST value of ≥ 500 IU/L or an increase in direct, indirect, or total bilirubin of ≥ 2 x ULN,
 - Serum creatinine increase of > 1.5 x the baseline value (and final serum creatinine value is $> \text{ULN}$).

